1. COMBINATION THERAPY DOSE ESCALATION

This appendix provides details of the design that will guide the dose-escalation of RO7296682 in combination with atezolizumab and its operating characteristics through simulations. All analyses were performed using the R statistical software version 3.5.3 (2019-03-11; [R Core Team, 2017](#)).

2. RATIONALE FOR MODEL-BASED DESIGN

The modified continuous reassessment method (mCRM) design uses a statistical model that actively seeks a dose level close to the maximum tolerated dose (MTD) by using toxicity data from all enrolled evaluable participants to compute a precise dose-toxicity curve. It locates the MTD efficiently and minimizes the number of participants treated at possibly pharmacological inactive dose levels. Such model-based designs have been successfully applied in many Phase 1 dose-escalation studies ([Schöffski et al. 2004](#); [Le Tourneau et al. 2009](#); [Neuenschwander et al. 2008](#)). The simulations in this appendix investigate the operating characteristics of the design as implemented for this study.

In this design, the MTD is defined as the dose maximizing the posterior probability that the dose-limiting toxicity (DLT) rate π (MTD) $\in [0.2, 0.33]$ while keeping the probability of overdose $\{p(\text{MTD}) > 0.33\} < 0.25$.

3. STATISTICAL MODEL

A two-parameter logistic model will be used to fit the dose-toxicity relationship. The probability of DLT at dose d_j , $p(d_j)$ is defined as (1)

$$p(d_j) = \frac{\exp(\alpha + \beta x_j)}{1 + \exp(\alpha + \beta x_j)} \quad (1)$$

where

$$x_j = \ln\left(\frac{d_j}{d^*}\right)$$

and d^* is the reference dose (in this case $d^* = \boxed{\text{ }}$ mg)

The model (1) thus can be rewritten as (2):

$$\ln\left(\frac{p(d_j)}{1 - p(d_j)}\right) = \alpha + \beta x_j \quad (2)$$

where α and β are the parameters to be estimated and assumed to follow a bivariate normal distribution.

3.1 GENERAL MODEL SETTING

3.1.1 Dose Grid

The following dose grid has been used:

From █ by █; from █, by █; from █ by █.

3.1.2 Maximum Dose Increments

The following rules for selecting the maximum allowed dose increment will be applied.

- Maximum Dose Increments relative to DLT:
- In absence of a DLT a dose increment of 200% is allowed (i.e., next dose could be as high as 3-fold the previous dose)
- After the first DLT has been observed, the maximum allowed dose increment is reduced to 100% (i.e. up to 2-fold) for later cohorts. If there is only 1 accumulated DLT, no DLT in the most recent 2 cohorts, and provided the current dose is less than █ mg, it is allowed to switch back to a dose increment of 200% (i.e. up to 3-fold). Otherwise, the maximum dose increment of 100% (i.e. up to 2-fold) remains.
 - In addition, based on the emerging data from the single agent dose-escalation study (WP41188), the upper limit to allow switching back to a dose increment of 200% (i.e. 3-fold) will be reset to 6-fold lower than single agent MTD.
- After 2 accumulated DLTs have been observed, a dose increment of 100% (i.e. 2-fold) must be maintained for all subsequent cohorts.

3.1.3 Stopping Rules

The algorithm will recommend ending the dose-escalation if any of the following criteria applies:

- Enough information on MTD:

At least a minimum of 12 participants evaluated and at least 6 participants have been accrued near the MTD dose (where near means differing from the MTD by at most 10%)

and the posterior probability that the MTD dose lies within the target toxicity interval is above 50% **OR**

- Maximum dose is safe:

at least 6 subjects have been observed at the maximum dose or near (differing from the maximum dose by at most 10%) and it is at least 50% likely that the probability of a DLT for the maximum dose is below 0.2. **OR**

- Maximum number of participants:

The maximum sample size of 60 DLT evaluable participants has been reached.

3.2 MODEL PRIOR

A minimally informative bivariate normal prior for the parameters of the DLT dose response curve (α , β) is constructed in order to have a weak impact on the final MTD determination ([Neuenschwander et al. 2008](#)).

This minimally informative prior “neutral” component will be constructed based on the assumed not toxic and toxic dose levels. It is conservatively assumed that it would be unlikely (less than 10% confidence) that a 15% or higher DLT rates are associated with the first dose (█ mg) of RO7296682 in combination with atezolizumab and that it would be very unlikely (less than 10% confidence) that a 35% or lower DLT rate are associated with the dose of █ mg.

[figure not shown]
The parameters of the minimally informative prior are listed below (3):

$$\begin{aligned}\mu &= (\alpha, \beta) = (0.05, 0.59) \\ \Sigma &= \begin{pmatrix} \sigma_{\alpha}^2 & \sigma_{\alpha\beta} \\ \sigma_{\alpha\beta} & \sigma_{\beta}^2 \end{pmatrix} = \begin{pmatrix} 1.99701 & 0.05136 \\ 0.05136 & 0.00188 \end{pmatrix} \quad (3)\end{aligned}$$

where μ and Σ are the parameters of the bivariate normal distribution.

The prior distribution used to determine the dose-escalation decision for this study is shown in [Figure 2](#).

Figure 2 Minimally Informative Prior

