4.1.2 Dose Escalation Decision Criteria

The decision to escalate will be made by the Safety and Dose Escalation Committee (SDEC), as described in [Appendix 11](#). The SDEC is composed of key Sponsor-based functional representatives and study investigators (see Section [4.1.4](#)) and will meet regularly during Part I. Details on the SDEC are available in the SDEC charter.

In Part I, a modified continual reassessment method (mCRM) with escalation with overdose control (EWOC) will guide the dose escalation to determine the MTD ([Neuenschwander et al. 2008](#)). The decision to escalate (or not) to the next dose level will be made when at least three participants in a cohort will have completed the DLT period, following the review of all relevant safety information collected.

The dose-DLT relationship will be described by a Bayesian two-parameter logistic model where the probability of DLT is a function of dose (for further information, see [Appendix 11](#)). The model will be used:

- To estimate the MTD (defined as the dose with the highest probability that the DLT rate is within the target interval of 20% to 33%, and a probability less than 25% to be associated with a DLT rate superior to 33%).
- To recommend a dose for the next cohort complying to pre-specified safety rules (e.g., dose increments from one cohort to the next bounded to 200%). These safety rules are detailed in [Appendix 11](#).

A minimally informative bivariate normal prior for the parameters of the DLT dose-response curve is constructed for this model in order to have a weak impact on the final MTD determination. For the dose-toxicity relationship, it is conservatively assumed that it would be very unlikely that 15% or higher DLT rates are associated with the first dose of RO7296682 in combination with atezolizumab and that a 35% or lower DLT rate is associated with maximum planned dose of RO7296682.

The model will be continuously updated as new participant information becomes available, including data collected during the DLT period for the current cohort and data collected during the treatment period from the previous cohorts.

Dose-Escalation Process

The DLT period starts from the first administration of RO7296682 and atezolizumab and ends 7 days after the second administration of RO7296682 and atezolizumab. To remain DLT evaluable, a delay in receiving the second dose of maximum 2 days can be allowed if agreed by the SDEC.

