9.4.3 Safety Analyses

Unless otherwise specified, all safety analyses listed in [Table 15](#) will be based on the safety population. All safety parameters will be analyzed using descriptive statistics, summarized and presented in tables. Data will be summarized by dose and regimen (if applicable) within each part.

Table 15 Safety Statistical Analysis Methods

Endpoint	Statistical Analysis Methods
Adverse events	
The original terms recorded on the eCRF by the Investigator for AEs will be coded by the Sponsor.
 
Adverse events will be summarized by mapped term and appropriate thesaurus level. The severity of AEs will be graded according to the NCI CTCAE v5.0. Toxicity grade, seriousness, and relationship to study treatment will be presented, as well as summaries of deaths, AEs leading to death and premature withdrawal from study treatment. A glossary of AEs, medication(s), and procedures will be provided.

Clinical laboratory tests	All clinical laboratory data will be stored in the database in the units in which they were reported. Laboratory test values will be presented in International System of Units (SI units; Système International d'Unités) by individual listings with flagging of abnormal results.
Vital signs	Vital signs data will be presented by individual listings with flagging of values outside the normal ranges and flagging of abnormalities. In addition, tabular summaries will be used, as appropriate.
ECG data analysis	ECG data will be presented by individual listings. In addition, tabular summaries will be used, as appropriate.
Concomitant medications	
The original terms recorded on the participant's eCRF by the Investigator for concomitant medications will be standardized by the Sponsor by utilizing a mapped term and appropriate drug dictionary level.
 
Concomitant medications will be presented in summary tables and listings.

Nature and frequency of DLTs	DLT events will be presented by individual listings. The MTD will be estimated with an mCRM-EWOC using DLT evaluable participants. The MTD estimate will be presented along with 90% Credible Intervals.

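### The dose-escalation prior is weak on the intercept but all but fixes the slope, so the promised 90% credible interval for the MTD is conditional on a slope near 0.59

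*Combined protocol and SAP*

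**What the plan says.** Section 4.1.2 states: "A minimally informative bivariate normal prior for the parameters of the DLT dose-response curve is constructed for this model". Appendix 11, Section 3.2 repeats the label and says that the prior "is constructed in order to have a weak impact on the final MTD determination".

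Appendix 11, Section 3 gives a two-parameter logistic model in x = ln(d/d*), "where α and β are the parameters to be estimated and assumed to follow a bivariate normal distribution". The normal prior is thus placed on β itself, not on its logarithm. Section 3.2 prints prior means of 0.05 for α and 0.59 for β, with covariance rows "1.99701 & 0.05136" and "0.05136 & 0.00188". It says that the prior was built from two tail statements. One is that it is "unlikely (less than 10% confidence) that a 15% or higher DLT rates are associated with the first dose". The other is that it is "very unlikely (less than 10% confidence) that a 35% or lower DLT rate are associated with the dose of" a redacted amount.

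Table 15 in Section 9.4.3 commits to an interval: "The MTD estimate will be presented along with 90% Credible Intervals". The simulation criteria in Appendix 11, Section 4.2 cover the MTD chosen, DLT proportions, overdosing, duration and sample size, but not interval coverage. The visible text neither justifies the slope variance nor plans a sensitivity analysis on it.

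**The concern.** A prior described as having little influence should let the data determine both parameters. A slope variance of 0.00188 is very small for a logistic slope on log dose. If the slope is settled in advance, the model learns where the curve sits but not how steep it is. Steepness is what converts uncertainty about the DLT rate into uncertainty about dose, so it sets the width of the MTD interval. A reader told that the prior has a weak impact would take that interval as a statement of what the trial showed, when much of its width is assumed.

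**Working it through.** **Inputs** (Appendix 11, Section 3.2): mean(α) = 0.05, mean(β) = 0.59, var(α) = 1.99701, cov = 0.05136, var(β) = 0.00188. Maximum sample size is 60 DLT-evaluable participants (Section 3.1.3).

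**1. The plan's tail statements.** Under the prior, logit p(x) is normal with mean 0.05 + 0.59x and variance 1.99701 + 2(0.05136)x + 0.00188x².
- The first statement reaches exactly 10% at x = −5.66, that is d = 0.0035 d*.
- The second reaches exactly 10% at x = 2.10, that is d = 8.2 d*.
- Both hold if the two doses are at least about 2,360-fold apart (8.194/0.003471). The doses and d* are redacted, so this cannot be confirmed or refuted.

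**2. How tight each parameter is.**
- Intercept SD = √1.99701 = 1.413. The 95% range for the DLT rate at d* is logit⁻¹(0.05 ± 1.96 × 1.413), or 6% to 94%. This is weak.
- Slope SD = √0.00188 = 0.0434, or 7.3% of the mean. The 95% range is 0.59 ± 1.96 × 0.0434 = 0.505 to 0.675.
- Correlation = 0.05136/(1.413 × 0.0434) = 0.838.
- Slope SD given the intercept = 0.0434 × √(1 − 0.838²) = 0.024.
- If the prior were meant for ln β, the slope would be just as tight: exp(0.505) to exp(0.675), or 1.66 to 1.96.

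**3. What the trial can add.** Prior precision of the slope = 1/0.00188 = 532. Data information is approximately n·p(1 − p)·Var(ln dose). Assume n = 60, p = 20%, and a log-dose SD of 1 or 2:
- SD 1: 60 × 0.2 × 0.8 × 1 = 9.6, and 9.6/(532 + 9.6) = 2%.
- SD 2: 60 × 0.2 × 0.8 × 4 = 38.4, and 38.4/(532 + 38.4) = 7%.

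Simulated trials on an assumed dose grid agree. For true slopes from 0.2 to 2.5, the mean posterior slope stayed between 0.56 and 0.61.

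**4. Consequence for the interval.** A difference u on the logit scale becomes a dose ratio of exp(u/β). The target window of 20% to 33% has u = logit(0.33) − logit(0.20) = 0.678.
- Across the prior slope range, the model takes this window to be exp(0.678/0.675) = 2.7-fold to exp(0.678/0.505) = 3.8-fold wide in dose.
- The actual window would be 9.6-fold wide at slope 0.3 and 2.0-fold wide at slope 1.0.

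Two invented data sets illustrate the effect, taking the MTD as the dose with a 26.5% DLT rate (an assumption, because the plan names no point target). The comparator has the same intercept prior and an independent log-normal slope with median 0.59 and log-SD 1.
- Steep data (no DLTs in 15 participants at low doses, then 1/12 and 6/12): 90% interval 11- to 12-fold wide with the plan's prior, 2.7-fold with the flexible slope.
- Flat data (1/6 at each of four low doses, then 3/12 and 3/12): 7- to 8-fold with the plan's prior, about 900-fold with the flexible slope.

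The plan's interval is of similar width in both cases. The posterior slope under its prior is 0.57 in the first and 0.58 in the second; the flexible prior gives 2.3 and 0.27.

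**The case against.** The strongest reply is that the plan claims weak impact on the MTD, not on the slope, and that the prior on the MTD's location is indeed diffuse. At the 26.5% target its prior 90% interval spans about 2,000-fold in dose. In simulation on an assumed grid, the median estimated MTD was 0.98 to 1.12 times the true value for slopes of 1 or more. At slope 0.3 it was 0.38 to 0.65 times the true MTD, but at that slope the lower ratio corresponds to a true DLT rate of logit⁻¹(logit 0.265 + 0.3 ln 0.38) = 21%, still inside the target range. This stands: the claim is fair for location and inaccurate for slope and interval width.

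A reader might infer that the 90% interval is simply miscalibrated. The documents do not support that. On the assumed grid, coverage was 90% to 92% when the true slope was 0.59, 57% to 73% at slope 0.3, and 99% or more at slopes of 1 and above. In a separate check with data concentrated around the MTD it stayed at 88% to 92%. The answer turns on the true slope, the redacted doses and where participants are treated.

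A reader might also infer that the fixed slope sends participants to overly toxic doses. That is not shown either. Overdose control requires less than 25% probability that the DLT rate exceeds 33%, which would block a step to a dose modelled near that limit. Increments narrow after the first DLT. The seven simulated scenarios evaluate the chosen prior, and their results are redacted rather than absent.

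Finally, the stakes are limited. Section 4.2.2 subjects model output to clinical judgment, Section 4.3.3 rests the Part II dose on PK/PD modelling, and no visible decision uses the MTD interval. This also stands, and it is why the remedy concerns reporting only.

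**Conclusion.** The description of the prior is wrong for one of its two parameters. The slope is held near 0.59 (SD 0.043), and up to 60 participants contribute about 2% to 7% of the information on it. This follows from the printed matrix; the percentages also assume a DLT rate near 20% and a log-dose SD of 1 to 2. The interval promised in Table 15 is therefore conditional on that slope. It can be too narrow if the true curve is much flatter, and it is wider than necessary if the curve is steeper. The direction and size in this trial are unknown, so none of the simulated coverage figures should be cited as the design's performance. The point is worth correcting because it changes what the reported interval can be taken to mean. It is not evidence that the escalation is unsafe.

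**What to change.** - Confirm that 0.00188 and the scale of β are printed correctly. If they are, give the reason for so tight a slope.
- In Appendix 11, Section 3.2 and in Section 4.1.2, describe the prior as weakly informative on the intercept with a near-fixed slope.
- Leave the escalation model unchanged. A flexible slope used to drive escalation has its own cost: in one simulated scenario (true slope 0.3, MTD at 0.135 d*) it stopped 210 of 600 trials early for toxicity, against 12 of 600 with the plan's prior.
- At the final analysis, report the MTD and its 90% credible interval also under a slope-flexible prior as a sensitivity analysis. One option is a log-normal slope with median 0.59 and log-SD about 0.8, with the same intercept prior. State the DLT rate that defines the MTD for the interval, and state that the primary interval is conditional on the near-fixed slope.

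The cost is one extra model fit and a few sentences, with no added participants and no change in conduct. The drawback is that the sensitivity interval may be much wider if the data suggest a flat curve. The flexible prior also reduces the dependence on the slope assumption without removing it.

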3.3 MODEL PERFORMANCE EVALUATION

To illustrate how the design will perform, different escalation scenarios were explored and the corresponding results are tabulated in [Table 1](#). Each column represents four different situations: which dose would the model recommend, after seeing no DLTs in previous cohorts and when 0, 1, 2, or 3 DLTs are observed in the current cohort. The evaluation is based on cohort size = 3, where stop indicates that the model would stop escalating and the study would be halted.

In general, if there are no observed DLTs, the model will suggest to escalate close to what the maximum increments allow, while in presence of one DLT the increments are more limited (see [Table 1](#)). With 2 or 3 DLTs, the model always recommends to de-escalate or STOP. Therefore, the results show that the design will adequately adapt the dose in the presence of observed DLTs.

Table 1 Dose Escalation Mock Runs

Dose Level	Dose (mg)	Next Dose (% Increment) if no DLT	Next Dose (% Increment) if 1 DLT	Next Dose (% Increment) if 2 DLTs	Next Dose (% Increment) if 3 DLTs
1					
2					
3					
4					
5					
6					
7					
8					

[figure not shown]

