4.2.2 Rationale for the mCRM-EWOC Design

Part I dose escalation will be carried out according to a mCRM-EWOC design and based on the occurrence of DLTs. The mCRM-EWOC design has many favorable characteristics:

- It adaptively fits a dose DLT response curve by incorporating toxicity data from eligible participants among different cohorts, and preclinical or clinical information from compounds with similar modes of action via the prior.
- The design also locates the MTD more efficiently, without pre-specifying exact dose levels for each cohort. Dose selections are made based on the DLT dose response curve measured by a 2 parameter logistic model over the dose range, subject to clinical judgment and mandated safety constraints that limit the size of dose increments. Moreover, the EWOC algorithm highly reduces risks of exposing participants to overly toxic doses. Of note, the model provides only the upper limit for recommended dose. A dose lower or higher than the model recommended dose may be selected based on clinical judgment.

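### Appendix 11: the printed prior, the stated first-dose calibration and the claim that 2 of 3 DLTs always lead to de-escalation or STOP cannot all be true

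*Combined protocol and SAP*

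**What the plan says.** Appendix 11, section 3, defines a two-parameter logistic model in the log of dose over a reference dose, whose intercept and slope "are the parameters to be estimated and assumed to follow a bivariate normal distribution". Section 3.2 prints the prior mean (0.05, 0.59) and a covariance matrix with rows "1.99701 & 0.05136" and "0.05136 & 0.00188". It says the prior is built on the view that "it would be unlikely (less than 10% confidence) that a 15% or higher DLT rates are associated with the first dose". Protocol section 4.1.2 puts the same point more strongly: "it would be very unlikely that 15% or higher DLT rates are associated with the first dose of RO7296682".

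Section 4.1.2 defines the MTD as the dose most likely to have a DLT rate of 20% to 33%, subject to "a probability less than 25% to be associated with a DLT rate superior to 33"%; Appendix 11, section 2, repeats this. Section 3.3 then describes mock runs with cohorts of 3 and no DLTs at earlier levels, and reports: "With 2 or 3 DLTs, the model always recommends to de-escalate or STOP". It concludes that the design adapts the dose adequately when DLTs occur. In that section STOP means that the study would be halted, so repeating a dose is neither de-escalation nor STOP.

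**The concern.** The sentence is absolute, and the conclusion about adequate adaptation rests on it. The printed prior, however, gives the first dose a very low expected toxicity and has a fairly small spread there. With such a prior, 2 DLTs in 3 participants may not move the posterior far enough to breach the 25% limit.

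If so, the SDEC and ethics committees are told of a model safeguard that the printed settings do not provide at the lowest doses, in the first participants to receive this combination. The effect is on what they can rely on the model to do. It is not automatic re-dosing: the SDEC decides each dose, and section 4.2.2 says "Of note, the model provides only the upper limit for recommended dose".

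**Working it through.** **Inputs.** Prior mean (0.05, 0.59); var(α) = 1.99701, cov = 0.05136, var(β) = 0.00188 (Appendix 11, 3.2). Model: logit p = α + βx, with x = ln(dose / reference dose). Calibration: P(p ≥ 0.15 at first dose) < 0.10. Overdose limit: P(p > 0.33) < 0.25. Target interval: 0.20 to 0.33. Cohort size 3.

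**Step 1: locate the first dose without the mg values.** Under the prior, logit p at x is normal with

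- mean m(x) = 0.05 + 0.59x
- variance s²(x) = 1.99701 + 2(0.05136)x + 0.00188x²

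The 10% bound solves m(x) + 1.2816·s(x) = logit(0.15) = -1.735. The solution is x = -5.663, where m = -3.291 and s = 1.215. Check: -3.291 + 1.2816 × 1.215 = -1.734. A tail below 10% needs a lower x.

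**Step 2: posterior at the first dose after 2 of 3 DLTs.** With θ = logit p, the posterior density is proportional to φ(θ; m, s)·e^(2θ) / (1 + e^θ)³. Integrating above logit(0.33) = -0.708 gives P(p > 0.33) = 0.2387, below 0.25. One-dimensional quadrature and two-dimensional grid integration agree. Varying the printed parameters within their rounding gives 0.238 to 0.239.

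**Step 3: is the same dose preferred?** After 2 of 3 DLTs at the bound:

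| Dose relative to first dose | P(p > 0.33) | P(0.20 ≤ p ≤ 0.33) |
|---|---|---|
| 0.5 | 0.107 | 0.215 |
| 0.75 | 0.177 | 0.257 |
| 1.0 | 0.239 | 0.275 |

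Target-interval probability is still rising at the current dose. The overdose limit is reached only at 1.05 times that dose.

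**Step 4: can another rule force STOP?** Of the three criteria in section 3.1.3, one needs at least 12 evaluated participants, one needs 6 at or near the maximum dose, and one needs 60 participants. None can be met after one or two cohorts of 3 at low doses. After two DLTs, section 3.1.2 only caps the next increment at 2-fold.

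**Step 5: other starting points and levels.** P(p > 0.33) at the current dose after 2 of 3 DLTs, with 0 of 3 at earlier levels and 3-fold steps:

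| First dose x | Prior tail | Level 1 | Level 2 | Level 3 | Dose ceiling at level 1 |
|---|---|---|---|---|---|
| -5.663 | 10% | 0.239 | 0.243 | 0.286 | 1.05× |
| -6.0 | 7.2% | 0.194 | 0.207 | 0.254 | 1.29× |
| -6.25 | 5.6% | 0.164 | 0.182 | 0.231 | 1.51× |

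At level 2 and the bound, target-interval probability is 0.312 at the current dose against 0.182 one level down, so the model again does not step down.

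**Step 6: cases that agree with section 3.3.** At the bound, 3 of 3 DLTs at the first dose gives 0.574, and 2 of 3 DLTs gives 0.286 or more from level 3 up. These lead to de-escalation or STOP as stated.

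**Step 7: break-even.** P(p > 0.33) after 2 of 3 reaches 0.25 at the first dose when x = -5.58, a prior tail of about 10.8%. For level 2 with a 3-fold step, the starting tail must be about 10.6%. Both exceed the stated limit of less than 10%.

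**The case against.** **The 10% may be only an elicitation target.** Section 3.2 words it as an assumption used to build the prior, not as a tail computed from the printed parameters. A fitted tail of 10.8% would remove the level 1 conflict. That is possible, but section 3.2 would then be untrue of the prior it introduces, so the conflict moves rather than disappears.

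**The margin is thin.** It is 0.011 at level 1 and 0.007 at level 2. Appendix 11 does not say how posteriors were computed. With 1,000 effective posterior draws, a true 0.2387 would be estimated at 0.25 or more about 20% of the time, so simulation error could have put STOP in the sponsor's table. This stands as an explanation of how the sentence may have arisen. It does not make it true, and the bound is the case most favourable to the sentence.

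**The slope may be log-normal.** With the same numbers on that scale, level 1 gives 0.270, which is STOP. But sections 3 and 3.2 both say bivariate normal. The log-normal reading also implies only a 13-fold range between the two calibration doses, which sits poorly with eight mock-run levels. The normal reading implies about 2,360-fold, close to seven 3-fold steps (3^7 = 2,187).

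**Table 1 and the doses are redacted.** This limits what can be said: the level 1 result assumes that mock-run level 1 is the first dose of section 3.2. Level 2 also depends on the step size; a 4-fold step would give 0.294, although section 3.1.2 caps the step at 3-fold.

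**Practical effect is limited.** The SDEC reviews all safety data and may choose a lower dose. This stands, and it is why the point concerns a correction to Appendix 11 rather than a change of design.

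**Conclusion.** The concern holds. Taken literally, the printed prior, the less-than-10% calibration and the 25% overdose limit contradict the section 3.3 sentence for 2 of 3 DLTs at the first dose. P(DLT rate > 33%) is at most about 0.239 and falls as the calibration tail falls. At level 2 with a 3-fold step from the bound it is 0.243. In both cases the model permits the dose to be repeated.

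The failure is confined to 2 DLTs at the lowest levels: levels 1 and 2 at the bound, and level 3 as well if the tail is as low as 5.6%. The conclusion assumes that the calibration statement applies to the printed prior, that the slope is normal as stated, and that the mock runs start at that first dose. It does not identify which of the three statements is wrong.

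**What to change.** Re-run the Table 1 mock runs with the printed prior and the 25% limit, and state the prior probability of a DLT rate of 15% or more at the first dose. Then do one of two things:

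- replace the absolute sentence in section 3.3 with the model's behaviour by level, noting that 2 of 3 DLTs at the lowest levels may allow the dose to be repeated; or
- correct the printed prior or the section 3.2 calibration statement (and its counterpart in section 4.1.2) so that the sentence holds.

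No dose or clinical rule needs to change. The cost is a re-run of existing R code and a wording correction, with no effect on participants or procedures.
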